#### 7.3.3.5. Ophthalmology Assessment

The following ophthalmology examination findings will be summarized by treatment cohort and overall for each timepoint and eye (left and right), using counts and percentages:

Normal/Abnormal Not Clinically Significant not related to underlying condition/Abnormal Not Clinically Significant related to underlying condition/Abnormal Clinically Significant for the following:

- Adnexa, Eye Movements, Intraocular Pressure
- Visual Acuity
- Slit-lamp Biomicroscopy categories: Anterior Chamber, Lens, Conjunctiva, Cornea, Fundus, Other

Is Visual Acuity impacted by any abnormality observed' (yes/no)

Listings of all ophthalmology assessments will be provided by treatment cohort, patient identification, and visit, including any free text response for 'Findings' where calcifications should be noted.

#### 7.3.3.6. Pregnancy

Pregnancy data will be provided in a listing by treatment cohort and patient identification.

#### 7.3.3.7. Anti-Drug Antibodies and Neutralizing Antibodies

The following frequency counts and/or percentages will be provided for ADA:

- Frequency counts of patients who were missing all ADA values at Baseline, had ADA values at Baseline, missing all ADA values post-baseline, had ADA values post-baseline, or had ADA values present both at Baseline and post-baseline.
- Frequency counts and percentages of patients who were "ADA Negative" or "ADA Positive" at Baseline. The denominator will be the number of patients who had ADA values reported at Baseline.
- Frequency counts and percentages of patients who were:
  - "Always ADA Negative"
  - "Ever ADA Positive"
  - "ADA Positive Continuously"
  - "ADA High Titer Category (>128)"

The denominator will be the number of patients who had ADA values reported postbaseline.

- Frequency counts and percentages of patients who were "ADA Negative" or "ADA Positive" at Baseline (in patients who had ADA values reported at both Baseline and post-baseline). The denominator will be the number of patients who had ADA values reported both at Baseline and post-baseline.
- Frequency counts and percentages of patients that had ADA values reported who were:
  - "Always ADA Negative"
  - "Ever ADA Positive"
  - "ADA Positive Continuously"
  - "ADA High Titer Category (>128)"

The denominator will be the number of patients who had ADA values reported at both Baseline and post-baseline.

- Frequency counts and percentages for shifts in ADA status from:
  - "ADA Negative" to "Always ADA Negative"
  - "ADA Negative" to "Ever ADA Positive"
  - "ADA Positive" to "Always ADA Negative"
  - "ADA Positive" to "Ever ADA Positive"
  - "ADA Negative" to "ADA Positive Continuously"
  - "ADA Positive" to "ADA High Titer Category (>128)"

The denominator will be the number of patients who had ADA Status reported at both Baseline and post-baseline.

The following frequency counts and/or percentages will be provided for NAb:

- Frequency counts of patients who were "ADA Positive" at baseline or "Ever ADA Positive" at post-baseline. This summary will identify the population of patients for relevant assessment of NAb.
  - Frequency counts of patients who were missing all NAb values at Baseline, or had NAb values at Baseline, and patients who were "ADA Positive" at baseline.
  - Frequency counts and percentages for "NAb Negative" and "NAb Positive" at Baseline in patients who were "ADA Positive" at Baseline. The denominator will be the number of patients who had NAb values at Baseline and were "ADA Positive" at Baseline.
  - Frequency counts of patients who were missing all NAb values at post-baseline, or had NAb values at post-baseline, and patients who were "Ever ADA Positive" post-baseline.
  - Frequency counts and percentages for "Always NAb Negative" and "Ever NAb Positive" post-baseline in patients who were "Ever ADA Positive" post-baseline. The denominator will be the number of patients who had NAb values post-baseline and were "Ever ADA Positive" post-baseline.

The number and percentage of patients that do and do not develop ADA to asfotase alfa at each time point will also be presented. Additionally, descriptive statistics for ADA titers at each time point will be presented, including counts and percentages for each titer, and median, minimum, and peak titer. For those patients that are ADA positive, the number and percentage of patients

with NAb positive and negative status will be presented along with continuous descriptive statistics for the NAb % inhibition for NAb positive patients.

The peak ADA titer and last ADA titer will be summarized with descriptive statistics, as well as the peak NAb and last NAb % inhibition in the patients that are both ADA and NAb positive overall. The peak and last NAb % inhibition will be evaluated only in results that have both ADA and NAb positive status.

The following will be summarized descriptively: the time to first post-baseline ADA positive, the time to first post-baseline ADA positive continuously, the time to first ADA peak titer, the time to first ADA high titer category (>128), the time to first NAb positive, and the time to first NAb peak % inhibition. Finally, graphical displays will be presented showing titer levels over time, with an overlay of PPi and (separately) PLP levels over time. Listings of all antibody data will be produced by treatment cohort, patient identification, and visit.

Graphical displays will be presented as appropriate.

# 9. **APPENDICES**

# 9.1. **Protocol Schedules of Events**

### Table 2: Protocol Schedule of events

		Run-in	Main Study Period						Safety F/U Call 		
Assessment	Screeni ng	Period	Single Dose	No Dosin g	V	Weekly Dosing (3x/week) No Dosing					
Study	W -12	D -7 to	D1-	D8-	D15-D	D36-	D43-	D57-	D64-D8	D81-	EOS+
$Dav^{2,3}$	to	D -1	D7	D14	35	D42	D56	D63	0	D87	3m
Study	W -2	(W -1)	(W1)	(W2)	(W3-	(W6)	(W7-	(W9)	(W10-	(W13	0111
Week 		(" 1)	()	()	W5)	(110)	W8)	()	W12)	)	
Informed					((2))		(10)		((12)	)	
Consent 	Х										
Inclusion/											
Exclusion	Х										
Criteria											
Demograph	v										
ics 	Х										
Medical	v										
history 	Λ										
HPP gene											
mutation		Х									
analysis 											
Concomita											
nt	x	x	x	x	x	x	x	x	x	x	
medications		21						21			
°											
Concomita	37	37				37		37		37	
nt	Х	Х	Х	Х	Х	Х	Х	Х	X	Х	
therapies											
Physical	v	v	v					v		v	
examinatio	Λ	Λ	Λ					л		Λ	
Vital											
signs 	Х	Х	Х	Х	Х		Х	Х	Х	Х	
Body											
Weight 	Х	Х	Х	Х	Х	Х	Х	Х	X	Х	
Randomizat											
ion		Х									
In-Clinic 	X	X	X					X		X	
Study drug											
administrati											
on-Single			Х								
Dose 											
Study drug											
administrati											
on-3x					Х	Х	Х	Х			
Weekly											
Dosing 											
Chemistry,											
hematology	Х		Х					Х		Х	
, 14											
urinalysis 			1								

		Run-in	Main Study Period						Safety F/U Call 		
Assessment	Screeni ng	Period	Single Dose	No     Dosin     Weekly Dosing (3x/week)     No Dosing							
Study	W -12	D -7 to	D1-	D8-	D15-D	D36-	D43-	D57-	D64-D8	D81-	EOS+
Day 	to	D -1	D7	D14	35	D42	D56	D63	0	D87	3m
Study Week 	W -2	(W -1)	(W1)	(W2)	(W3- W5)	(W6)	(W7- W8)	(W9)	(W10- W12)	(W13	
Lab Tests (vitamin D, serum PTH, urine Ca:creatini ne) 	X		X					X	(12)	X	
Pregnancy Test	Х	Х	Х					Х		Х	
Renal ultrasound		Х								Х	
Eye exam 		Х								Х	
Pharmaco- dynamics (PPi and PLP) 	Х	Х	х	х	Х		Х	Х	Х	Х	
Anti-drug antibodies 			Х	Х	Х		Х	Х	х	Х	
Pharmacoki netics 			Х	Х	Х		Х	Х	Х	Х	
Adverse events 				X – Continuous Monitoring							

Abbreviations: EOS = end-of-study; F/U = follow-up; AE = adverse event; HR = heart rate; IAR = injection-associated reaction; PK = pharmacokinetics; PLP = pyridoxal 5'-phosphate; PPi = inorganic pyrophosphate; PTH = parathyroid hormone; m = month; W = Week; d = day.

**NOTE:** Patients may be asked to provide additional blood samples at an unscheduled visit at the request of the Sponsor or Investigator as part of a safety evaluation or for adjustment of the drug dose.

 The Safety Follow-Up Call will occur 3 months after the last dose of study drug. Males and Females of child-bearing potential will be followed up for birth control and pregnancy information. Any reported pregnancies in female patients or female partners of male patients will be followed until the outcome of the pregnancy is known. Refer to Section 9.4.1.10 for further details.

 The Week 1, Day 1 single dose must be administered on a Monday, and the multiple dosing must be administered on Mondays, Wednesdays, and Fridays during the weeks indicated.

 To facilitate scheduling of required study assessments at each visit, the study visit may be shortened or prolonged, as necessary, as long as the specified order of assessments and/or availability of results pertaining to laboratory work (including PK and pregnancy and asfotase alfa anti-drug antibody testing) and vital signs are adhered to.

 If the time period between the initial Screening and the re-Screening is >12 weeks, all Screening procedures must be repeated.

 Demographics will be collected as permitted by region and may include Date and region of birth, age, sex, ethnicity, race, and whether the patient is of Japanese descent.

 Medical history includes general medical history and HPP-specific medical history from historical medical records (eg, X-rays, videos, hospitalization records). Details of loss of adult teeth will be included as part of medical history.

 HPP gene mutation analysis will be performed at Baseline if results (from within 49 days of Baseline) are not available in the medical records.

 Concomitant medications and therapies must be collected from 30 days prior to study entry up until the final study visit. All available historical use of certain medications (ie, related to HPP, growth, etc.) will be captured.

 Physical examination will include assessment of general appearance; skin; head, ear, eye, nose, and throat; neck; lymph nodes; chest; heart; abdominal cavity; limbs; central nervous system; musculoskeletal. At Screening and Baseline visits, a complete physical examination will be performed. Thereafter, limited physical examinations (based on the patient's signs/symptoms) may be performed. All physical examinations (complete and limited) will include weight (using a calibrated scale) and examination of asfotase alfa injection sites for potential reaction(s). The Screening and Baseline physical examination will include height (using a wall-mounted standiometer).

-  Vital signs include blood pressure, heart rate, respiratory rate, and temperature. On dosing days in the clinic or under medical supervision at home, vital signs will be taken within 10 minutes before study drug injection.
-  In-clinic or inpatient study visits will occur during Screening, the Run-In Period (Week -1), Week 1, Week 9, and Week 13.
-  Urine and serum pregnancy testing is required for women of childbearing potential only. Results of urine pregnancy testing must be negative prior to IP administration (when applicable).
- Study drug will be administered in the clinic for the first dose and all other doses that occur during study visits. All other study drug administration will occur at home under the supervision of home healthcare.
-  All patients are required to fast for 8 hours prior to laboratory testing (water all ad libitum). All urine and blood samples for laboratory assessments must be collected prior to study drug administration. Single exception is blood sample collection for analysis of PK parameters at required post-dose timepoints. For all patients, fasting samples should be collected at the beginning of the visit day, before any other study-related procedures are performed.
-  A full ophthalmology examination will be performed at scheduled visits. The examination will assess for papilledema and signs of ectopic calcification, and will include assessments of visual acuity; adnexa; and slit-lamp biomicroscopy with examination of anterior chamber, lens, conjunctiva, cornea, and fundus. The ophthalmology examination should be performed by a qualified ophthalmologist. Sites will be provided ophthalmologic worksheets required to complete the full exam. Ophthalmology exams may be performed by a qualified optometrist (i.e., Doctor of Optometry, O.D.) as long as the optometrist works under the supervision of an ophthalmologist.
-  Asfotase alfa anti-drug antibody testing and PK/PD analyses must be performed on samples obtained at the same time (ie, predose samples from the same study visit).
-  Refer to Table 3 for timing of PK/PD and asfotase alfa anti-drug antibody assessments.
-  For acute or severe IARs (eg, with signs/symptoms of hypersensitivity, irrespective of the time from administration of study drug to onset), additional blood and urine samples must be collected to assess the reaction. Refer to Section 9.5 for details of sample collection.

				PK, PPi	
	Week	Sampling Times	Dosing 	and PLP	ADA
Run-in	Week -1	Day -7: -168h, -156h pre-dose	NA	PPi and	NA
Period	(establish	Day -1: -24h, -12h pre-dose		PLP only	
	baseline)				
Single	Week 1	Day 1: pre-dose; post-dose 6h, 12h	D1 (single-	All	Day 1: pre-dose
Dose			dose)		
No Dosing	Week 1	Day 2: post-D1 dose 24h, 32h, 36h	None	All	
		Day 3: post-D1 dose 48h, 56h, 60h			
		Day 4: post-D1 dose 72h			
		Day 5: post-D1 dose 96h			
		Day 6: post-D1 dose 120h			
		Day 7: post-D1 dose 144h			
No Dosing	Week 2	Day 8: post-D1 dose 168h	None	All	Day 8: post-D1 dose
0		Day 11: post-D1 dose 240h			168h
Weekly	Week 3	Day 15: pre-dose, post-dose 6h	D15, D17,	All	Day 15: pre-dose
Dosing			D19		
(3 times	Week 4	Day 22: pre-dose, post-dose 6h	D22, D24,	All	Day 22: pre-dose
per week)			D26		
	Week 5	Day 29: pre-dose (trough), post-	D29, D31,	All	Day 29: pre-dose
		dose 6h	D33		
	Week 6	None	D36, D38,	None	None
			D40		
	Week 7	Day 43: pre-dose (trough), post-	D43, D45,	All	Day 43: pre-dose
		dose 6h	D47		
	Week 8	Day 50: pre-dose (trough), post-	D50, D52,	All	Day 50: pre-dose
		dose 6h	D54		
	Week 9	Day 57: pre-dose	D57, D59,	All	Day 61: pre-dose

# Table 3: Protocol schedule of events for Pharmacokinetic, Pharmacodynamic, andImmunogenicity Assessments

	Week	Sampling Times	Dosing 	PK, PPi and PLP	ADA
		Day 61: pre-dose (trough), post- dose 6h, 12h, 24h, 32h, 36h, 48h, 56h, 60h	D61		
No Dosing	Week 10	Day 64: post-D61 dose 72h Day 65: post-D61 dose 96h Day 66: post-D61 dose 120h Day 67: post-D61 dose 144h Day 68: post-D61 dose 168h	None	All	Day 68: post-D61 dose 168h
	Week 11	Day 71: post-D61 dose 240h Day 75: post-D61 dose 336h	None	All	Day 75: post-D61 dose 336h
	Week 12	Day 80: post-D61 dose 456h	None	All	Day 80: post-D61 dose 456h
	Week 13	Day 87: post-D61 dose 624h	None	All	Day 87: post-D61 dose 624h

Abbreviations: ADA = anti-drug antibodies; PK = pharmacokinetics; PLP = pyridoxal 5'-phosphate; PPi = inorganic pyrophosphate; SOM = Study Operations Manual; D = day; h = hour, NA=not applicable.

NOTE: Trough is defined as pre-dose concentration (ie, concentration data-point collected just prior to the next dose). NOTE: Baseline definitions:

• For PD assessments, there are 5 pre-treatment baseline samples (-168, -156, -24, -12, and pre-dose Day 1) to be collected. The average value will be used for Baseline.

• For PK and immunogenicity assessments, Baseline is Day 1 pre-dose sample.

1 Timepoints for pre-dose PK sample collection have a window of -15 minutes and for post-dose PK sample collection have a window of  $\pm 15$  minutes. For additional instructions, please refer to the SOM.

2 The Week 1, Day 1 single dose must be administered on a Monday, and the multiple dosing in Week 3 through Week 9 must be administered on Mondays, Wednesdays, and Fridays.

#### 9.2. Sample Size, Power, and Randomization

A sample size of 9 patients per cohort (27 patients total) will provide sufficient power (>80%) to detect a difference of 2.3 µM between the 9.0 mg/kg/week cohort compared to the 1.5 mg/kg/week cohort, and between the 6.0 mg/kg/week cohort compared to the 1.5 mg/kg/week cohort in the change from Baseline to pre-3PrdP dose in Week 9 PPi (assuming a SD of 1.5 μM). This is based upon the use of a 2-sided, 2-sample t-test analyzed using a fixed sequence testing procedure with the comparison of the 9.0 mg/kg/week cohort compared to the 1.5 mg/kg/week cohort being performed first, and the hypothesis testing for the second comparison 6.0 mg/kg/week cohort compared to the 1.5 mg/kg/week cohort only being performed if the null hypothesis is rejected for the previous comparison at a significance level of 0.05.

A sample size of 6 patients per cohort (18 patients total) will provide sufficient power (>90%) to detect a difference of 3.2 µM (SD 1.5 µM) using the same assumptions and fixed sequence testing procedure. A difference of 3.2 µM (SD 1.5 µM) was observed in adult pediatric-onset treated patients versus controls in Study ENB-009-10 for the change from baseline to Week 6 in PPi. Between 6 and 9 patients per cohort (18 and 27 patients total) will give sufficient power to detect a mean difference of 2.3 to 3.2 µM (SD 1.5 µM).

27 patients who meet eligibility criteria for study participation will be randomized to 1 of the following 3 cohorts:

1. 0.5 mg/kg initial single dose; multiple dosing starting after 2 weeks at 0.5 mg/kg 3 times per week

2. 2.0 mg/kg initial single dose; multiple dosing starting after 2 weeks at 2.0 mg/kg 3 times per week

3. 3.0 mg/kg initial single dose; multiple dosing starting after 2 weeks at 3.0 mg/kg 3 times per week

Randomization will be stratified by gender to ensure a similar distribution of gender in each cohort. An IXRS central randomization scheme will be employed.

# 9.3. Technical Specifications for Derived Variables

The following derived data will be calculated prior to analysis.

#### Age

Age will be presented as the number of years between date of birth and the reference date. The following ages may be computed, with reference dates indicated:

#### Age and reference date

AC	Æ	RF	CFERENCE DATE
•	Age at Diagnosis	•	Date of Diagnosis
•	Age at First Known Sign/Symptom	•	Date of Onset of First Known Sign/Symptom
•	Age at Enrollment	•	Date of Signing ICF
•	Age at First Injection	٠	Date of First Injection

In cases where only the month and year are provided for a date, the day for the date will be imputed as 15. Missing month will be imputed as June. In cases where the day is observed but the month is missing, the date will be imputed as June 15. In instances when the imputed reference date is earlier than the birth date, the birth date will be used as the reference date.

#### Time Since Reference date

TIME	REFERENCE DATE				
Time Since First Known	Date of Onset of First Known Sign/Symptom				
Sign/Symptom					
Time Since Diagnosis	Date of Diagnosis				

Time Since First Known Sign/Symptom and Time Since Diagnosis are based on first dose date, will each be dichotomized into the following categories: < 10 years and  $\ge 10$  years.

#### **Definition of Treatment Baseline:**

• For PPi and PLP assessments, there are 5 pre-treatment baseline samples (-168, -156, -24, -12h, and pre-dose Day 1) to be collected. The average value will be used for Baseline.

• For antibody, and laboratory assessments, Treatment Baseline is the Day 1 pre-dose sample.

• For Safety assessments (including weight), the last assessment prior to first dose will be used for Treatment Baseline.

#### **Adverse Events**

Additional details for the analysis of Adverse Events described in Section 7.3.2:

Treatment-emergent AEs (TEAEs) are events with start dates and start times on or after the date and time of the first study drug dose. If the start date of an AE is partially or completely missing and the end (stop) date and time of the AE does not indicate that it occurred prior to first dose, then the determination of treatment-emergent status will be based on the following:

If the start year is after the year of the first study drug dose, then the AE is treatment-emergent; else,

If the start year is the same as the year of the first study drug dose and the start month is missing, then the AE is treatment emergent; else if the start month is present and is the same or after the month of the first study drug dose, then the AE is treatment-emergent; else, if the start date is completely missing, then the AE is treatment-emergent.

Pre-Treatment Adverse Events (PTAEs) are the AEs occur after the time of informed consent up through the Run-In Period and prior to the 1st dose.

Patient percentages are based on the total number of treated patients in the particular treatment cohort.

Related AEs are defined as possible, probable or definitely related, or events with missing relationship status. Unrelated AEs are defined as unlikely or not related.

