## 9.4.1. Adverse Event

An AE is any untoward medical occurrence in a patient or clinical study subject administered a medicinal product and which does not necessarily have a causal relationship with this treatment. An AE can therefore be any unfavorable or unintended sign (for example, an abnormal laboratory finding), symptom, or disease temporally associated with the use of a medicinal product, whether or not considered related to this medicinal product.

Exacerbation of a chronic or intermittent pre-existing condition including an increase in frequency and/or intensity of the condition, and abnormal laboratory findings that are considered to be of clinical significance are all considered to be AEs.

The definition of an AE also covers medication errors and uses outside what is foreseen in the protocol, including misuse and abuse of the product.

Situations where an untoward medical occurrence did not occur (social and/or convenience admission to a hospital), and anticipated day-to-day fluctuations of pre-existing disease(s) or condition(s) present or detected at the start of the study that do not worsen are not AEs.

High ALP levels detected through clinical laboratory testing will not be considered an AE after initiation of the study drug as these reflect circulating levels of asfotase alfa.

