## 9.4.1.4. Recording Adverse Events

All observed or reported AEs regardless of treatment or causal relationship must be recorded and reported as described in Section 9.4.1.11.

For all AEs, the Investigator must obtain adequate information for the following:

- 1. Determine the outcome of the AE
- 2. Determine if the event meets criteria for an SAE
- 3. Assess the severity of the AE
- 4. Determine the causality of the AE

For all AEs, regardless of casual relationship, the Investigator must follow-up on the outcome of the event until the event or sequelae either resolve or stabilize.

Adverse events spontaneously reported by the patient, and/or parent or legal guardian and/or identified in response to an open-ended question from study personnel, or revealed by observation will be recorded during the study phase by the Investigator. Adverse event information will be collected from the signing of informed consent until completion of the study.

Adverse Events must be documented in clear, unambiguous medical terms. Study personnel are advised not to use abbreviations or acronyms.

For each AE record only the diagnosis on the AE page of eCRF, do not report the characteristic signs and symptoms of the diagnosis as additional AEs.

If a diagnosis is not available, record each sign and symptom as an AE, when a diagnosis becomes available, study personnel are to update the AE page of the eCRF with relevant diagnosis only.

Change in severity of an AE should be documented based on specific guidelines in the eCRF Completion Guidelines.

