#### 7.3.2. Adverse Events (AEs)

Adverse events will be coded in MedDRA and presented by SOC and PT. Adverse events occurring on or after first treatment, treatment-emergent AEs (TEAEs), will be tabulated and presented by treatment cohort and overall. Summaries for pre-treatment AEs (PTAEs) will be included only where appropriate and specified. See Appendix 9.3 of the SAP for further details on the difference between TEAEs and PTAEs. Study displays to be included are described below.

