#### 7.3.2.1. Overall Summary of Adverse Events

An overall summary of the following categories of AEs will be presented by treatment cohort and overall, including summaries of events (n) and number of patients with events (n, %): TEAEs, treatment-emergent SAEs, and treatment-emergent non-SAEs. Within each category, the following subcategories will also be summarized:

- Mild/Moderate/Severe TEAEs
- Related TEAEs (possibly, probably, definitely related, or missing relationship)
- TEAEs leading to withdrawal from the study
- TEAEs leading to death
- AESI, see Section 7.3.2.7

A summary of events (n) and number of patients with events (n, %) for PTAEs will also be included with the following subcategories: Mild/Moderate/Severe AEs, AEs leading to withdrawal, and AEs leading to death (note that Related AEs and AESI do not apply to PTAEs).

A listing of all TEAEs by treatment cohort and patient will be presented. Separate listings will be produced for treatment-emergent SAEs, AEs leading to study drug withdrawal, AEs resulting in death, and PTAEs.

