#### 7.3.2.4. AEs and SAEs by SOC, PT, and Relationship

The number and percentage of patients with events will be presented by SOC and PT by grouped relationship (related, not related). If a patient has more than one occurrence of an AE, the strongest relationship to study treatment will be used in the summary table.

In addition, the number of AEs and the number and percentage of patients with AEs will be summarized by SOC and PT, and relationship result: not related, unlikely related, possibly related, probably related, or definitely related.

Lastly, the number of Related TEAEs and the number and percentage of patients with Related TEAEs will be summarized by SOC and PT, and separately by PT. The same analysis will be produced for Related treatment-emergent SAEs.

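### The SAP's TEAE definition has no worsening clause, so an AE that starts before Day 1 and worsens on drug is classed as pre-treatment if it is kept as one record

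*SAP*

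**What the plan says.** **Definition.** SAP Appendix 9.3 (Adverse Events): "Treatment-emergent AEs (TEAEs) are events with start dates and start times on or after the date and time of the first study drug dose". The stop date matters only when the start date is incomplete. SAP 7.3.2 says "Adverse events occurring on or after first treatment, treatment-emergent AEs (TEAEs), will be tabulated and presented by treatment cohort and overall" and refers back to the appendix. The protocol uses the term TEAE in its synopsis but does not define it.

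**Pre-treatment events.** Protocol 9.4.1.4: "Adverse event information will be collected from the signing of informed consent until completion of the study". SAP Appendix 9.3 names the pre-dose portion: "Pre-Treatment Adverse Events (PTAEs) are the AEs occur after the time of informed consent up through the Run-In Period" and before first dose. Neither statement says what happens if such an event worsens later.

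**Where PTAEs appear.** SAP 7.3.2: "Summaries for pre-treatment AEs (PTAEs) will be included only where appropriate and specified". SAP 7.3.2.1 gives them their own block in the overall summary (severity, withdrawal, death) with the remark "note that Related AEs and AESI do not apply to PTAEs", and a separate listing. SAP 7.3.2.2 adds an SOC/PT table. The Related tables of SAP 7.3.2.4 are limited to TEAEs: "the number of Related TEAEs and the number and percentage of patients with Related TEAEs will be summarized by SOC and PT".

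**Recording of worsening.** Protocol 9.4.1 counts as an AE "Exacerbation of a chronic or intermittent pre-existing condition including an increase in frequency and/or intensity of the condition". Protocol 9.4.1.4 and 9.4.1.7 send changes in an AE's severity to the eCRF Completion Guidelines.

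**The concern.** Safety and tolerability is the secondary objective (Protocol 5.2), and the TEAE tables are its main display. If classification depends only on when a record starts, an event that was mild before dosing and became severe or serious on drug can be counted against the pre-treatment period. Its relationship to study drug would then not appear in the Related-TEAE tables. For events that sites keep as a single record, the error runs one way: TEAE, severe-TEAE and Related-TEAE counts can only be too low.

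The SAP is also uneven. It resolves completely missing start dates, and same-year dates with no month, towards treatment-emergent. It has no rule for a worsening whose date is known. The count therefore depends on a recording convention that the SAP neither states nor cites.

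**Working it through.** There is no stated figure to reproduce. The check traces one event through the rules and then gives the scale.

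**1. Can a PTAE carry post-dose outcomes?** SAP 7.3 places all safety analyses on the Safety Set, and SAP 6.3 limits that set to patients with at least one dose. SAP 7.3.2.1 nevertheless plans PTAE rows for withdrawal and death. A patient in that set who withdrew or died did so after being dosed. So the SAP's own layout allows an on-study outcome to be filed under a pre-treatment event.

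**2. One event, two recording practices.** Take a symptom that starts in Run-in, is mild and ongoing on Day 1, and becomes severe during multiple dosing.

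| | Worsening kept in the original record | Worsening entered as a new record |
|---|---|---|
| Start date under Appendix 9.3 | before first dose | after first dose |
| Class | PTAE | TEAE |
| TEAE and severe-TEAE summaries | no | yes |
| Related-TEAE tables (7.3.2.4) | no | yes, if judged related |
| AESI line of the overall summary (7.3.2.1) | no | yes, if an AESI |
| PTAE tables and listing | yes, at worst severity if the record was updated | yes, for the earlier mild record |

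The patient's course is the same in both columns. Only site practice differs.

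**3. Which column applies?** The documents do not settle it.
- Towards one record: Protocol 9.4.1.4 and 9.4.1.7 treat a change in severity as a feature of an AE, and 9.4.1.4 has each AE followed until it resolves or stabilizes.
- Towards a new record: Protocol 9.4.1 makes exacerbation of a pre-existing condition an AE. Protocol 9.3.1 to 9.3.5 require clinically significant changes on examination, vital signs, laboratory tests, eye examination and renal ultrasound to be recorded as AEs.
- Not directly covered: a symptom, such as pain, already recorded as an AE after consent and then worsening on drug.

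**4. Time in which such events can arise.** Screening runs from Week -12 to Week -2, followed by Run-in in Week -1.
- Longest pre-dose period: 12 × 7 = 84 days.
- If Screening falls at the start of Week -2: 2 × 7 = 14 days.
- For comparison, the main study period runs from Day 1 to Day 87.

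**5. Weight of one patient.** Percentages use treated patients in the cohort (SAP 7.3.2.2).
- 27 patients over 3 cohorts gives 9 per cohort: 1/9 = 11.1 percentage points.
- If a cohort had only 6 treated patients: 1/6 = 16.7 points. Six is the planned minimum of completers, so 9 is the relevant denominator if enrolment goes to plan.

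These are upper limits per patient. Someone who already has another event in the same row moves that row by nothing.

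**The case against.** The strongest reply is that the eCRF Completion Guidelines may already require a new record, with its own date, when an AE worsens. If so, the worsening is a TEAE under Appendix 9.3 as written. This stands: the misclassification is conditional, and the documents cannot show that it will happen.

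Several narrower replies also stand.
- A reader might infer that hypersensitivity could be hidden this way. It could not. Protocol 9.4.2.1.1 defines injection-associated reactions as occurring within 3 hours after study drug, and 9.4.2.1.2 ties injection site reactions to the site of administration. Neither can begin before first dose.
- Ectopic calcification is largely covered where a clinically significant change from Baseline on eye examination or renal ultrasound is recorded as an AE (Protocol 9.3.4, 9.3.5).
- Ordinary day-to-day fluctuation of existing disease that does not worsen is not an AE under Protocol 9.4.1. This shrinks the pool of pre-dose AEs.
- No event disappears. PTAEs are tabulated and listed. The listings of AEs leading to drug withdrawal or death carry no treatment-emergent limit. The five-level relationship table in 7.3.2.4 and the AESI tables in 7.3.2.7 are worded loosely enough that their scope is uncertain.
- Safety is descriptive with no hypothesis tests (SAP 7.3), and an AE with missing relationship counts as related.

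None of this supplies the missing rule. It narrows the gap to an AE that is new after consent, ongoing at first dose, worsens outside the change-from-Baseline provisions, and is kept as one record.

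**Conclusion.** The TEAE definition is incomplete. An AE that starts between consent and Day 1, is ongoing at dosing, and increases in severity or becomes serious on drug will be a PTAE if the worsening stays under its original record. It would then be left out of the TEAE, severe-TEAE and Related-TEAE summaries and the AESI line of the overall summary, which can understate those rates.

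The size is up to 11.1 points per patient in a cohort of 9, assuming no other event for that patient in the row. How many patients would be affected is unknown, because the documents give no rate of pre-dose AEs that later worsen.

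A reader might go further and conclude that every such AE stays pre-treatment, so that the safety rates are biased downward. The documents do not support that. It depends on eCRF guidelines that are not provided, and several protocol provisions point towards a separate AE entry.

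**What to change.** 1. In SAP Appendix 9.3 and 7.3.2, define a TEAE as an AE that starts on or after first dose, or that starts before first dose and increases in severity or becomes serious on or after it. Count it once, at its post-dose severity and relationship.
2. Apply the same definition to the Related and AESI summaries (SAP 7.3.2.1, 7.3.2.4, 7.3.2.7), and state the scope of the AESI tables and the five-level relationship table explicitly.
3. Align the eCRF Completion Guidelines so that a post-dose worsening is captured with its own date, and link it to the earlier record so that it is not counted twice.

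The cost is one clause in the SAP, matching wording in three subsections, and one line in the guidelines. TEAE counts may rise slightly. In return they no longer depend on how a site records a change in severity.
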